## **Data Collector Protocol**

#### **Data Collection Protocol**

On the event grid within REDCap it will display all the records including questionnaires, form by form, for the particular events for one Participant ID. There is a "legend for status icons", where you can view the status of each form which can guide "work flow" for a particular participant. Listed are the questionnaire forms that will be collected at each point of data collection.

Questionnaire Forms	Baseline	~6 Week Post-	20 Week Post-
	Phone Call	Partum	Partum
Demographics	X		
Health	X		
Weight Change Goals PhenX Toolkit	x		X
Breastfeeding Benefits	x		
IFPS II	x		
IPAQ	x		X
Breastfeeding Self-Efficacy Scale	X	X	X
Edinburgh Depression Scale	X	X	X
HBSS	X	X	X
Fruit And Vegetable Inventory			
PSQI	X		X
Phenx Fiber Intake	X		x
Phenx Healthy Food Environments	X		X
Phenx Physical Activity Neighborhood Environment	x		x
Breastfeeding Intensity		X	X
Repeated Weight Measure		X	X
Checklist Baseline Data Collection	X		
Checklist 6Wk Postpartum Home Visit		X	
Checklist 20Wk Postpartum Home Visit		Contraction of the Contraction o	Х

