# Kerver Randomization process Logistics (Ruised

#### **RANDOMIZATION PROCESS/LOGISTICS**

- 1. BRIC
   Prepare randomization table

   Packet ID# (sequential)/ group assignment (T or C)

   Randomization scheme: block randomization with random block size
- 2. BRIC Email randomization table to [name]/[name]'s supervisor, [name]. [[name] and her supervisor are-is unblinded.]
- 3. [name] Create packets

Insert appropriate material (T or C) based on the randomization table. Label with Packet ID# on outside of packet. Deliver packets (in numerical order) to Data Collectors (DCs)

4. DC Complete baseline data collection.

Retrieve next numbered packet. Use packets in sequential order. On Checklist Baseline Data Collection Phone Call FORM enter the Packet ID# for each Participant. Address the Packet with the Participant's mailing address.

Record on the paper log sheet for each Packet ready for mailing: PacketID#/Participant Initials/Date packet mailed

5. [name]?? View the Packet GroupAssnmnt REPORT on a daily basis. Open the Intervention FORM for each Participant listed in the report and enter the Group Assignment (T or C) for the given Packet ID#, by using the randomization table. Note: The report and form are blinded to all but [name] and Interventionists

6. Interventionist

View the Ready for Intervention Scheduling REPORT on a daily basis. Participants listed in the report are ready to be schedule for intervention visits. *Note: This report is blinded to all but [name] and Interventionists.*  Comment [JK1]: Does [name] also have access?

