#### Analysis Plan:

**Aim 1: Feasibility of recruitment and retention:** Feasibility will be assessed at multiple points: enrollment rate (percent of eligible and approached women); percent of participants for whom study staff is notified of hospital admission for birth; percent of participants completing each additional data collection point. By compartmentalizing our feasibility assessment in this R21 exploratory/developmental project, we will be better able to target specific areas for refinement to inform our planned phase III trial. Retention will be assessed by the percent of participants who complete the 20 week postpartum data collection visit.

**Aim 2:** Acceptability will be measured at each data collection point using a brief questionnaire developed by the research team that will allow participants to rate the value and utility of the intervention content and give their opinions about the format, ease of use, and delivery method. Control group participants will be asked a similar set of questions to compare satisfaction with usual care practices. Engagement will be assessed as percent of intervention arm participants completing each planned intervention contact and by the frequency of log-ins to the online system, use of web/mobile-based tracking tools, and interactions with peer counselors. Feasibility and acceptability will be assessed separately from, but also in relation to the primary outcomes of breastfeeding duration and weight retention. For example, we will assess the number of women who discontinue BFing but continue tracking diet and exercise. These results will guide our structured interview questions planned for the final data collection visit (20 wks postpartum).

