Aim 3: Estimate the preliminary effect size of the intervention relative to a) the control group (at 20 weeks postpartum) and secondarily to b) patients in the same health system who are not enrolled in our study (via electronic medical records at 6 weeks postpartum) on: (1) breastfeeding duration, and (2) postpartum weight retention. Statistical Analyses: Subjects will be randomized to treatment (TRT) or control (CNT). Adequacy of the randomization: Randomization adequacy will be tested by comparing relevant baseline maternal and infant characteristics between the two study arms. Where substantive differences exist, they will be controlled for in subsequent analyses. We will test the degree of similarity, however, following Altman we will be guided by the degree of dissimilarity, not strict statistical significance. Outcomes and Analysis: The data on *n* participants are denoted by with outcome and explanatory variables in the *i*-th participant. The two main outcomes are: (1) Duration of breastfeeding assessed by number of days postpartum at infant weaning (possible range=0-140 d), and (2) Weight retention assessed by the ratio of the maternal weight at 20 weeks postpartum to the pre-pregnancy weight. Both outcomes are regarded as continuous and will be analyzed using linear models. If data are found to be skewed, a logarithmic or square-root transformation q will be applied to . To assess the effect of treatment on outcome we will fit the model and test the hypothesis where is the coefficient for the TRT group indicator, with CNT as referent. Results will be presented as (1) a point estimate and 95% confidence interval for, with and without regression-adjustment and (2) a standard two-sample t-test of  $_{\circ}H$ . Statistical Power: With a total sample size of 80 women randomized to TNT, CNT we can detect at least a moderate effect size of 0.65 (i.e., in units of standard deviation) with power of 80% (2sided test, alpha=0.05). Our objective, however, is the estimation of effect size rather than testing for significance.

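### The adjusted breastfeeding-duration estimate has no covariates fixed in advance, so the baseline self-efficacy score collected before randomisation is not assured a place in the model

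*Combined protocol and SAP*

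**What the plan says.** The Analysis Plan (Aim 3) treats breastfeeding duration, in days from 0 to 140, as continuous. It is analysed with a linear model containing a treatment indicator, with a log or square-root transformation if the data are skewed. On adjustment the plan says two things. First, baseline characteristics will be compared between arms, and those that differ substantively will be controlled for; the size of the difference decides this, not its significance. Second, "Results will be presented as (1) a point estimate and 95% confidence interval for, with and without regression-adjustment", together with a two-sample t-test. It names no covariate and does not rank the adjusted and unadjusted estimates. It adds that the aim is to estimate the effect size, not to test for significance.

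The questionnaire grid in the Data Collector Protocol marks the "Breastfeeding Self-Efficacy Scale" at the baseline phone call, at about 6 weeks and at 20 weeks. The Study Activities Timeline puts the baseline survey (28-32 weeks) above the randomisation row. In the randomisation logistics, step 4 has the data collector "Complete baseline data collection" and then take the next numbered packet. By design, therefore, each randomised woman has a score obtained before her allocation.

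**The concern.** A baseline variable that predicts the outcome reduces residual variance even when the arms are perfectly balanced on it. Choosing covariates by observed imbalance does not look for that property. A variable that differs by chance may be unrelated to duration, and one that predicts duration strongly may be balanced and so give the rule no reason to include it. A self-efficacy score specific to breastfeeding is a reasonable candidate predictor, but the stated rule does not secure its inclusion.

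Two things are at stake. One is precision: with 80 women the interval is wide, and its width is the natural measure of success for an aim concerned with estimation. The other is pre-specification: several adjusted estimates and one unadjusted estimate could each be presented as the main result, and the covariate set would be settled after the data are seen. The estimate is meant to inform a planned phase III trial.

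**Working it through.** **Inputs from the documents.** Size: "With a total sample size of 80 women randomized to TNT, CNT". Detectable effect: "at least a moderate effect size of 0.65 (i.e., in units of standard deviation"). Operating characteristics: "power of 80% (2sided test, alpha=0.05").

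**Assumptions.**
- Allocation is 1:1, 40 per arm. The logistics say only "Randomization scheme: block randomization with random block size".
- All 80 women are analysed. No dropout rate is given; retention is itself an outcome ("Retention will be assessed by the percent of participants who complete the 20 week postpartum data collection visit").
- The share of variance in duration explained by the baseline score (R²) is not in the documents. The range 0 to 0.30 is assumed.

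**Step 1: the plan's own figure.** For a two-sample t-test with n = 40 per arm and effect 0.65 SD, the noncentrality is 0.65 × √(40/2) = 2.907 on 78 degrees of freedom. Two-sided power at 0.05 is 81.9%, which agrees with the stated 80%. This calculation uses no covariate.

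**Step 2: unadjusted half-width, in SD units.** t(0.975, 78) × √(2/40) = 1.9908 × 0.2236 = 0.445.

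**Step 3: half-width with the score always in the model.** The residual SD is √(1 − R²). One degree of freedom is lost, and estimating the slope multiplies the variance by about 1 + 1/76:

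t(0.975, 77) × √(2/40) × √(1 + 1/76) × √(1 − R²) = 0.448 × √(1 − R²).

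| R² | Half-width (SD) | Ratio to 0.445 | Power at 0.65 SD |
|---|---|---|---|
| Unadjusted | 0.445 | 1 | 81.9% |
| 0 | 0.448 | 1.007 | 81.4% |
| 0.10 | 0.425 | 0.955 | 85% |
| 0.20 | 0.401 | 0.901 | 89% |
| 0.30 | 0.375 | 0.842 | 93% |

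**Step 4: break-even.** The two widths are equal when √(1 − R²) = 1/1.0068, that is R² = 0.013 (correlation about 0.12). With 64 women analysed the same formula gives 0.017. About 1.5% is a fair summary.

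**Step 5: a bounded outcome.** Simulated durations clipped to 0-140 days (assumed latent mean 70, SD 60; 4,000 trials per setting) gave mean half-width ratios of 0.964, 0.930 and 0.883 at latent correlations of 0.3, 0.4 and 0.5. The formula gives 0.960, 0.923 and 0.872 at those correlations. The gain survives, slightly reduced.

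**Step 6: losses.** With 64 analysed, the half-width goes from 0.500 to 0.478, 0.451 or 0.422 SD, and power from 73% to 76%, 81% or 86%, at R² = 0.10, 0.20 or 0.30. Both intervals widen, but their ratio hardly changes.

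**Step 7: standardisation.** Adjustment shrinks the residual SD. At R² = 0.20, an effect of 0.65 total SD would read as 0.65/√0.80 = 0.73 if divided by the residual SD. The same difference in days would then look larger to those planning the next trial.

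**The case against.** The plan already promises an adjusted estimate, and that promise is unconditional. Its imbalance rule says that differing variables will be controlled for; it does not say that nothing else may be. The equations in this section are also missing from the text available, so any covariate terms in the model line cannot be seen. A reader might infer that the plan bars the score unless the arms differ on it, or that duration will go unadjusted. The documents support neither reading. What stands is narrower: the covariates of a planned adjusted analysis are not named, the only stated selection rule is imbalance, and no estimate is designated as the main one.

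The score's prognostic value is also assumed. No passage gives its correlation with duration, and other baseline forms (the breastfeeding-benefits and IFPS II forms, demographics, health) could be candidates too. A reader might infer that the planned interval is certainly, or even probably, too wide. The documents do not establish that. The case rests on an asymmetry: a loss under 1% if the score is useless, against several percent gained if it predicts moderately.

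Finally, this is an exploratory project with feasibility and acceptability among its aims, and significance testing is not its objective. The power gains therefore carry little weight, and no stated decision would change. That limits the importance of the point but does not remove it, since a narrower interval serves the estimation aim directly.

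**Conclusion.** The point holds as a modest improvement that is almost free; it is not an error that invalidates the planned analysis. The stated power reproduces, and the unadjusted estimate and t-test remain valid. With 80 women the half-width would fall from 0.445 SD by about 4%, 10% or 16% at R² = 0.10, 0.20 or 0.30, and would rise by 0.7% at R² = 0. These figures rest on 1:1 allocation, complete follow-up, a linear relation on the analysis scale and an R² that the documents do not supply. Naming one main estimate in advance is worthwhile even if the precision gain proves small.

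**What to change.** Add to Aim 3 of the Analysis Plan:

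- The main estimate for breastfeeding duration comes from a linear model with arm and the baseline Breastfeeding Self-Efficacy total score, fitted whatever the observed baseline difference. The unadjusted estimate and the t-test are supportive.
- Only the baseline score is used. The 6- and 20-week scores are measured after randomisation, may be affected by the intervention, and must not enter the model.
- Any standardised effect size is expressed in the unadjusted (total) SD of the outcome, not the residual SD.
- Women with a missing baseline score stay in the analysis by a simple rule, such as imputing the mean baseline score. The rule is needed because step 5 of the telephone script allows an interrupted survey to be finished later.

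The cost is a few sentences and one degree of freedom. It requires no new data collection, no extra participants and no added burden.
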